 - iii. Pediatric Inhaler Adherence Questionnaire, a self (or in the case of this study, phone administered) survey of barriers to medication adherence
 - iv. Parent attitudes towards medications and barriers to adherence.
 - v. Changes in adherence barriers and behaviors to improve adherence over time
 - vi. The number of asthma related readmissions or revisits between study visits will be self-reported.

- vii. The number of missed school days between visits will be self-reported.
- viii. Provider satisfaction will be recorded using the pre-post surveys

B. Description of Population to be Enrolled:

- a. Children admitted to Children’s Hospital Colorado inpatient or emergency department with a primary diagnosis of asthma exacerbation.
 - i. Inclusion criteria-patients
 - 1. Age 6-17 years
 - 2. On a controller medication at baseline
 - ii. Inclusion criteria-providers
 - 1. Aged 18-70
 - 2. Caring for a patient that is enrolled in the study
 - iii. Exclusion criteria
 - 1. Primary language other than English or Spanish (smartphone application only available in these languages)
 - 2. Homeschooled or not in school
 - 3. Significant developmental delay, cystic fibrosis, interstitial lung disease, tracheostomy/ventilator dependence
 - 4. Following up with a pulmonary or allergy provider outside of the CHCO system

C. Study Design and Research Methods

The proposed study is a single center trial at Children’s Hospital of Colorado, designed to evaluate the effects of a navigator program on medication adherence, provider communication and other asthma related health outcomes. Participants will be recruited from the population of patients between the age of 6 and 17 years admitted to Children’s Hospital Colorado inpatient or emergency department with a primary diagnosis of asthma exacerbation. Investigators plan on a one-year enrollment period and will follow each study participant for 3-6 months.

Recruitment

Upon admission hospital staff will identify potential participants based on the admission medical record. Patients will be approached by research staff and asked if they would like to participate in the study. A member of the research team (principally, the research coordinator) will do the recruiting. The research coordinator will explain the study and enroll subjects. Estimated duration is 45-60 minutes depending upon the patient.

Consent/Assent

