We will obtain a signed parental permission form and an age-appropriate assent form for participants younger than 18 years. Consent will be obtained by a member of the research team (principally, the research coordinator or a research assistant). It will be made clear to patients that the research team is not part of the treatment team.

Study Design

We plan to enroll a total of 100 patients. and up to 400 providers. Patients enrolled will be provided and trained on using the adherence monitoring prior to discharge (sensors will be placed on discharge controller and quick-relief medication). Participants will also be enrolled in the smartphone application that will give them feedback about their medication usage. Once enrolled in the application, patients will receive push notification reminders to use their medications, as well as be able to access their adherence information in real time. Caretakers will also be given the

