option to have access to their child's adherence information. The smartphone application also has portions dedicated to education about asthma triggers. Patients will be set up with a pulmonary or allergy follow up within 2-4 weeks of discharge. Patient's pulmonary or allergy providers will also be enrolled in the propeller health system, with access to the propeller health dashboard. Once providers receive access, they will be able to log-in and view all of their patients in list format. They will be able to see up to the minute data on patient adherence at any time that they choose to log-in to the dashboard. Providers will also receive email notifications if their patient has not used their controller medications for 7 days, or if their patient has had a significant increase in quick-relief medication use, indicating a worsening of asthma status (see figure 1 below). Patients will be monitored for a total of 3-6 months. The asthma navigator will contact the families at 2, 4 and 6 months post-enrollment, and discuss the patient's recorded adherence with the families. If a patient is enrolled for 4-5 months, we will discuss adherence at 2 and 4/5 months. If a patient is only enrolled for 3 months, we will discuss adherence at 2 and 3 months. Additionally, they will discuss any barriers to adherence that the family may be experiencing, and make referrals to social work as necessary, as well as attempt to brainstorm ways to improve adherence with the families. Additionally, the asthma navigator will collect each patients' adherence data and create an adherence report, which will be distributed on a monthly basis to the patient's primary care provider, pulmonary/allergy provider, and school nurse via email. The asthma navigator will be monitoring communications between the providers and marking the numbers of communications.

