Demographic information including age, sex, race, and other baseline clinical information upon recruitment including duration of asthma, C-ACT score, ACT score, asthma symptoms, lung function, prescribed medication, and asthma related health care use in the previous year will be obtained at enrollment. The distributions of outcomes will be examined for normality using the Anderson-Darling Test. Dependent upon the distribution we will use the Wilcoxon rank-sum test, Mann-Whitney U test or paired T-test to test for significant changes in outcomes during the study period. Longitudinal patterns of adherence will be examined graphically.

Monthly rates of adherence, asthma symptoms, asthma control scores and monthly missed number of school days and number of hospitalizations will be calculated by study arm. Survey information from patients, caregivers, physicians and navigators on the navigator intervention will be reviewed by study staff and summarized qualitatively. Number of rehospitalizations will be obtained via chart review at 1 month, 6 months and 12 months post hospitalization.

The cost-effectiveness of the navigator intervention will be summarized based on medical resource utilization (direct) and loss of productivity (indirect). Medical resources utilization will include medical care resource utilization, asthma medication variables, navigator time and salary, while loss of productivity will be measured using the number of hours caretaker missed work due to participant's asthma, number of hours dependent participant missed school due to his/her asthma, and number of hours independent participant missed work due to his/her asthma. Unit costs will be applied to healthcare resources and loss of productivity and summed to obtain total costs for each subject. Average costs for the study group will be presented.

Power and Sample Size

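### The analysis called cost-effectiveness gives only one group's mean cost, averaged from per-subject totals with no stated time horizon

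*Combined protocol and SAP*

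**What the plan says.** The economic paragraph in Section IV.F (Data Analysis Plan) opens: "The cost-effectiveness of the navigator intervention will be summarized". It names a direct and an indirect component. For the direct one, "Medical resources utilization will include medical care resource utilization, asthma medication variables, navigator time and salary". The indirect one counts hours of work and school lost to asthma. Unit costs are applied and "summed to obtain total costs for each subject", and the planned output is the average for the study group. The paragraph gives no time window, no per-month rate and no handling of incomplete follow-up.

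On duration, Section IV.C says that the investigators "will follow each study participant for 3-6 months". Navigator contacts follow the same range: they are set at 2, 4 and 6 months, patients enrolled for 4-5 months have two, and "If a patient is only enrolled for 3 months, we will discuss adherence at 2 and 3 months".

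Section IV.E states that the study has one group, at the funder's request, and that comparisons are limited as a result.

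On technology, Section IV.C states that "sensors will be placed on discharge controller and quick-relief medication". It also describes the app and provider dashboard, and a hub for patients whose sensors do not sync. None of these is named in the cost list.

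**The concern.** There are two difficulties, and a smaller question of scope.

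First, a cost-effectiveness result needs a difference in cost set against a difference in effect. The plan produces one mean cost. A reader of the report could take the label as evidence of value for money that the design cannot give.

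Second, a total accumulated over 3 months and one accumulated over 6 are different quantities. Averaging them gives a number that shifts with how many patients happened to be followed for how long, even if the underlying cost of care is the same. A later study that wanted to use this pilot's cost figure could not tell what period it covers.

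The scope question is whether the cost of the intervention is meant to include the monitoring technology. The documents point both ways and the cost paragraph does not say.

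**Working it through.** The documents give no unit cost, cost standard deviation or cost result, so there is no stated figure to reproduce. The check compares the text and then works through the follow-up range.

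**1. Label against output (Sections IV.E and IV.F).** The label is cost-effectiveness and the output is the mean cost of one group. No comparator cost, incremental cost, effect denominator or ratio is planned. Health care use in the previous year is collected at enrolment, but nothing links it to the cost analysis.

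**2. Horizon.** Follow-up is 3-6 months (Section IV.C) and the cost horizon is unstated (Section IV.F). In the same section, adherence and missed school days are to be calculated as monthly figures; costs are not.

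**3. Contacts by duration (Section IV.C).** At 3 months there are two contacts (months 2 and 3). At 4-5 months there are two (month 2 and month 4 or 5). At 6 months there are three (months 2, 4 and 6). The monthly adherence reports also increase with time. Part of the navigator cost therefore rises with follow-up by design.

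**4. Range at a constant monthly cost c (assumed).** Total = c × months. The ratio of a 6-month to a 3-month total is 6c / 3c = 2.0. The group mean as a share of the 6-month cost is mean months / 6, so it lies between 3/6 = 50% and 6/6 = 100%.

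**5. Follow-up mixes (all assumed).** Table 1 in Section IV.A allows the later visits to fall at the end of the study. This suggests, without stating, that closure shortens follow-up for late enrollees. Suppose closure comes 3 months after the last enrolment. Patients enrolled before the last 3 months of accrual then get 6 months. Those enrolled evenly within the last 3 months average (6 + 3)/2 = 4.5 months.

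- Even accrual over the planned year: 9/12 = 75% get 6 months and 25% average 4.5. Mean = 0.75 × 6 + 0.25 × 4.5 = 5.625 months. Shortfall = (6 − 5.625)/6 = 6.25%.
- Ten per month, so 100 patients in 10 months: 0.70 × 6 + 0.30 × 4.5 = 5.55 months. Shortfall = 0.45/6 = 7.5%.
- Half of all patients enrolled in the last 3 months: 0.50 × 6 + 0.50 × 4.5 = 5.25 months. Shortfall = 0.75/6 = 12.5%.
- Mean follow-up of 4.5 months: 1.5/6 = 25%. Under this closure pattern, essentially every patient would have to enrol in the last 3 months.

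**6. Does dividing by months cure it?** Suppose that monthly cost halves after month 3 (assumed). The 3-month total is 3 × 1 = 3 and the 6-month total is 3 × 1 + 3 × 0.5 = 4.5, a ratio of 1.5. Cost per month is 3/3 = 1.00 against 4.5/6 = 0.75. A per-month figure alone would then still differ by follow-up length.

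**The case against.** **The horizon is silent, not wrong.** The plan never says that costs are summed over whatever time each patient was observed; that is the natural reading of its silence. Rehospitalizations are to be taken by chart review at 1, 6 and 12 months, so that component could be put on a common window. This stands, and it means that the defect is an unstated horizon rather than a demonstrated bias. It does not remove the difficulty, because navigator time remains tied to participation and nothing connects the chart-review windows to the costing.

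**A large downward bias.** A reader might infer from the 3-6 month range that the mean is seriously too low, for example by assuming that half or more of the patients stop at exactly 3 months. The documents do not support such a mix. They provide for 4-5 month patients and, if closure is what shortens follow-up, the shortfall is modest. Nor does the plan name 6 months as its cost target.

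**Omitted technology as an error.** A reader might also infer that leaving out devices is a mistake. Under the knowledge to be gained, the protocol frames the navigator as additional to electronic monitoring, so a navigator-only perspective is defensible. Hubs go only to patients with syncing trouble, and devices are to be returned, so full purchase price is not obviously a per-patient cost. Against that, the study supplies the devices, and Aim 1 compares with historical rates. What remains is a need to state the perspective.

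**The limitation is disclosed and cost is peripheral.** Section IV.E admits the lack of a control group. Cost appears in no aim, in no row of Table 1, and not under the knowledge to be gained. This lowers the importance of the point, but the label in Section IV.F is unchanged by the general disclosure.

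**Conclusion.** The point holds as a minor one. The label claims a property that the single-group design does not have, and this conclusion rests on the text alone. The unstated horizon makes the mean cost depend on the follow-up mix. At a constant monthly cost, individual totals can differ up to 2.0-fold through duration alone. The group mean would be about 6-8% below the 6-month cost under even accrual with closure 3 months after the last enrolment, and 25% below only if follow-up averages 4.5 months. These sizes rest on assumed accrual, closure and cost profiles, since the documents give no follow-up distribution and no costs. The documents do not show that the cost figure would be useless: an average cost with a stated horizon and perspective would be usable.

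**What to change.** In Section IV.F:

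- Call the analysis a cost description and make no cost-effectiveness claim.
- Report cost per patient-month as total cost divided by total months observed, with a bootstrap confidence interval that resamples patients. This matches the monthly figures already planned for other outcomes.
- Because costs may be front-loaded after discharge, also show the figure by follow-up interval, or give a censoring-adjusted 6-month mean. Restricting to the first 3 months looks simpler but does not fit the data collection: only patients enrolled for 3 months have a month-3 contact, and self-reported items are collected between visits.
- Show navigator cost as its own line.
- Give the total with and without monitoring technology (sensors, platform, and hubs where supplied), and state which perspective is the main one.

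The cost is a few sentences of plan text, unit costs for the technology, and slightly more analysis work. The claim becomes narrower and the stated cost somewhat higher.

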Breathing Counts
NCT03065205
Protocol version date 12.18.17

COMIRB Protocol

COLORADO MULTIPLE INSTITUTIONAL REVIEW BOARD
[name] [contact] [contact]

Protocol #: 16-1845

Project Title: Breathing Counts

Principal Investigator: [name]

Version Date: 12-18-17

I. Hypotheses and Specific Aims:

Adherence to asthma medications has been associated with good asthma control in children¹, however adherence to asthma medications is poor.² Children who are hospitalized due to their asthma are at a significantly high risk of re-hospitalization³, and represent a particularly high risk group. Successful control of asthma in a high-risk population requires a network of care providers who communicate relevant up-to-date information and support asthma control. Additionally, lay health worker interventions have been shown in some cases to decrease missed school days and parental work days.⁴ We propose to evaluate the efficacy of an asthma navigator program in a high-risk population of patients at Children's Hospital Colorado. We will evaluate the ability of the program to improve health outcomes of children who have asthma and who are at high-risk of re-hospitalization. The project will also evaluate the ability of the navigator program to increase the number of stakeholder communications amongst school nurses, program navigators, physicians, caregivers and children.

Specific Aim 1: Evaluate whether or not the addition of an asthma navigator to the current clinical standard of care will lead to sustainably increased levels of adherence compared to historical rates.

Hypothesis: By providing up to date adherence rates to the patient's medical care team and by addressing patient identified barriers, we hypothesize that the addition of an asthma navigator to the standard of care at Children's Hospital will increase asthma medication adherence rates, and that these adherence rates will be sustained over the 3-6 month monitoring period.

Specific Aim 2 Evaluate whether or not the addition of an asthma navigator results in increased levels of communication between PCPs, specialty providers and school nurses.

Hypothesis: The addition of an asthma navigator will result in increased emails and general communication between various providers in a patient's care team.

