The study is limited by time frame and funding for a one year recruitment period. The primary goal of the study is to provide preliminary information on the effect of a navigator program on the patient and caregiver response to asthma disease control. As a pilot and feasibility study, investigators have chosen to enroll a total of 100 patients and up to 400 providers. Through past clinical experience, we know that some months of the year are higher risk for asthma exacerbations, so we expect to screen more patients during the fall and winter than summer or spring. Considering the variable clinical case load Investigators plan on enrolling an average of 10 participants per month. Anticipating an enrollment rate of approximately 20% (in 2015, there were >600 asthma related admissions at Children's Hospital Colorado), investigators state they should be able to enroll up to 100 patients within one year. We plan to enroll up to 4 providers per patient with a simple pre-post survey as well.

The primary hypothesis of interest is to test whether change in adherence rates are different from zero. The smallest detectable difference was based on a paired sample t-test between pre and post adherence scores with a Type I error rate of 0.05 and 90% power. Based on previous studies⁸, investigators assumed a mean adherence rate of 50% with a standard deviation of 22%.

Table X:	
N	Δ
100	8%
65	10%
30	15%

Table X lists the smallest detectable difference (Δ) for by sample size. For the primary aim investigators will be able to detect a change of 8% or more in percent adherence during the study period with the available 100 patients.

F. Summarize Knowledge to be Gained:

- a. **Utility of an asthma navigator in addition to electronic adherence monitoring in improving adherence to asthma medications**
- b. **Utility of an asthma navigator in improving communication amongst all of a patient's medical providers**
- c. **Utility of an asthma navigator in improving other asthma control related outcomes.**

Asthma Control Classification

Control is computed based on taking the entry with the worst outcome in the following age-based tables:

Asthma Control Classification (Age 5-10)

(Age 5-11)	Asthma	Control	Classification
	Well controlled	Not well controlled	Very poorly controlled
Symptoms (manually entered)	≤ 2 days/week but not more than once on each day	> 2 days/week or multiple times on ≤ 2 days/week	Every day in previous week

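### Aim 1 asks for adherence above historical rates, but the planned primary test covers only within-study change, with 'pre' undefined and no historical comparison

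*Combined protocol and SAP*

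**What the plan says.** Section I, Specific Aim 1, asks whether adding a navigator "will lead to sustainably increased levels of adherence compared to historical rates". Its hypothesis adds that "these adherence rates will be sustained over the 3-6 month monitoring period". The aim therefore has two parts: an increase over a historical level, and durability.

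Section IV.F, Power and Sample Size, sets a different target: "The primary hypothesis of interest is to test whether change in adherence rates are different from zero". The sizing follows from it: "The smallest detectable difference was based on a paired sample t-test between pre and post adherence scores", where "investigators assumed a mean adherence rate of 50% with a standard deviation of 22" percent. The result is tied to the aim: "For the primary aim investigators will be able to detect a change of 8% or more in percent adherence during the study period".

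Section IV.F, Analysis plan, lists tests chosen by distribution "to test for significant changes in outcomes during the study period". It adds monthly rates and plots of adherence over time.

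On measurement, Section IV.C puts the sensors on the medication the child takes home at discharge. Table 1 in Section IV.A marks adherence at Visits 2, 3 and 4 but not at Visit 1. The enrolment data listed in Section IV.F include no adherence rate. The inhaler questionnaire in Section IV.A asks about barriers and does not give a rate.

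**The concern.** The primary test and the primary aim do not ask the same question. A paired test of change compares each child with himself or herself within the study. It contains no external reference, so it cannot show that adherence is above historical rates. No section names a historical rate, source or cohort as the comparator. The 50% in the sizing paragraph is a planning input, and the 28-73% range in Section II is background.

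The paired test also lacks a defined starting point, because device data begin only once the intervention package is under way. At stake are the interpretation of the main result and its prespecification. With both the 'pre' window and the historical value open, either could be chosen after the data are seen.

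**Working it through.** **1. The plan's own figure.** Inputs from Section IV.F: alpha 0.05 (two-sided assumed, since the hypothesis is a difference from zero), 90% power, SD 22, N = 100, 65 and 30. If 22 is the SD of the paired change, the noncentral t calculation gives detectable changes of 7.2, 9.0 and 13.5 points. Table X prints 8, 10 and 15. Those values arise at 95% power (8.01, 9.99, 14.99), or at 90% power with an SD of change near 24.5, and the document does not say which was used. This is a separate issue, and nothing below depends on it.

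**2. What the paired test can show.** Read 'pre' as early and 'post' as later on-device adherence. This is an inference, made because no other adherence rate is collected. Take 50% as an illustrative historical level.

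| Illustrative course | Against 50% | Paired change |
|---|---|---|
| 60% held throughout | +10 | 0 |
| 70% falling to 60% | +20, then +10 | -10 |

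Both courses lie above the historical level throughout, yet neither gives a positive paired result. The second matters because Section II reports that adherence tends to worsen over time even under monitoring. The fall would be a true finding about durability, but the test would not show whether adherence was still above historical rates.

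**3. What a historical comparison could detect.** Use a one-sample t-test of each child's whole-period mean against a value treated as known, with N = 100 and SD 22.
- Standard error: 22/√100 = 2.2.
- Detectable difference at 90% power: 7.2 points (normal approximation 3.24 × 2.2 = 7.1). Power for 8 points: 0.95.
- 95% CI half-width: 1.98 × 2.2 = 4.4 points.

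This takes 22 as the SD of the whole-period mean. If 22 is instead the SD of each of two windows weighted 1/3 and 2/3 (2 of 6 months, then 4), the SD of the mean is 22 × √(5/9 + 4r/9). The document gives no correlation r. Over r = 0 to 1 the SD runs from 16.4 to 22, and the detectable difference from 5.4 to 7.2.

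**4. When 8 points is no longer reached (SD 22, 90% power).**
- Fewer usable children: 82 are needed for 8 points. N = 80 gives 8.1 and N = 70 gives 8.6. Section IV.C anticipates syncing difficulties.
- An uncertain historical value: solve 3.24 × √(2.2² + SE²) = 8. Then SE² = (8/3.24)² - 4.84 = 1.26, so SE is about 1.1. For an assumed SE of 2 to 4, the detectable difference is 9.6 to 14.8.

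**5. Sensitivity to the chosen value.** An observed 60% is 32 points above 28%, 10 above 50% and 13 below 73%. If the untreated rate were really 55%, a test against 50% has noncentrality 5/2.2 = 2.27. It would be significant about 61% of the time with no effect of the programme.

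**6. Precision of the paired contrast.** If 22 is the SD of each window, the SD of change is 22 × √(2(1 - r)). At N = 100 the 95% CI half-width is 6.2, 4.4 and 3.4 points for assumed r = 0, 0.5 and 0.7.

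**The case against.** Several defences are fair.

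- **It is a pilot.** Section IV.F says "The primary goal of the study is to provide preliminary information on the effect of a navigator program", and Section IV.E concedes that the funder's single-group requirement limits comparisons. This stands as a reason for modest claims and lower severity. It does not define 'pre' or supply a historical value, and Section IV.E concedes only the lack of a control group.
- **The paired contrast is closer to the navigator question.** The section on knowledge to be gained asks what the navigator adds to electronic monitoring. A historical comparison cannot separate the navigator from the sensor, app and alerts. This also stands, and it is why restating the aim is a legitimate alternative remedy.
- **Monthly rates and plots will show the course.** They will, but without a historical reference.
- **The plan lists two-sample rank tests.** It applies them to change during the study, so they do not provide a historical comparison.

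A reader might go further and infer that the study is bound to miss its primary endpoint, because the paired test rejects only 5% of the time when adherence is flat. The documents do not support that. A test of no change always rejects at its alpha level when nothing changes. The early-versus-late reading is an inference, and a flat course is not what Section II leads one to expect. The figure shows that the two tests ask different questions and does not measure harm to this study.

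A reader might also infer that 100 children are too few for the historical question. With complete data and a known value they are not: 7.2 points is below the printed 8.

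**Conclusion.** The mismatch holds. As written, the plan leaves the increase over historical rates untested, and its paired test has no defined baseline. The paired test bears on durability and on change after navigator contact, but not on the historical part of Aim 1.

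The defect lies in wording and prespecification. The detectable difference of 7.2 points assumes 100 usable children, SD 22 for the whole-period mean and a historical value known without error. Losing more than 18 children, or a historical standard error above about 1.1 points, takes it past 8. That the test misses sustained high adherence rests on reading 'pre' as early device data.

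This should be fixed before the data are analysed. A higher rating is not justified for a single-group pilot that states its limits, and the Table X discrepancy should be handled separately.

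**What to change.** Before the data are analysed, choose one of two routes.

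**(a) Keep the historical aim.** Name and justify one historical value. The 50% is a candidate, but it is now only a sizing input. Report mean on-device adherence over the whole monitoring period against that value with a 95% CI, and show sensitivity across the cited 28-73%. State the detectable difference with its assumptions on usable N and the standard error of the historical value. Attribute the result to the whole package (sensor, app, alerts and navigator) and call it preliminary.

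**(b) Restate Aim 1 as within-study change** and drop the claim of an increase over historical rates.

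**Under either route**, define the paired windows in advance, for example months 1-2 (before the first scheduled navigator call) against later months. Report the estimate, its direction and the 95% CI. Judge whether adherence was sustained from the CI, not from a non-significant p-value. Note that app reminders, and possibly the monthly navigator reports, already run in months 1-2, so the early window is not free of intervention.

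**Cost.** Text changes only, with no new data from participants, although route (a) needs a source to justify the value. The Aim 1 claim becomes more modest. Under (a) it depends on the value chosen, as the 61% figure shows. Under (b) the historical question is given up.
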